# **3.4.3** INTERIM ANALYSES AND DATA MONITORING Interim analyses will not be conducted in this study.

## **3.4.4** MULTICENTER STUDIES

Although this study is a multicenter joint study, no related special analysis has been planned. Additional analyses will be planned after this study if necessary from the exploratory stand point.

#### **3.4.5** MULTIPLE COMPARISONS AND MULTIPLICITY

Adjustments for multiplicity will not be conducted in this study.

## **3.4.6** Use of an "Efficacy Subset" of Patients

In this study, the analysis for efficacy evaluation will be conducted in the per protocol set (PPS). The analysis will also be conducted in the full analysis set (FAS) as supplementary analysis.

## **3.4.7** ACTIVE-CONTROL STUDIES INTENDED TO SHOW EQUIVALENCE Not applicable in this study.

#### **3.4.8** EXAMINATION OF SUBGROUPS

In this study, the analysis of subgroups is planned. Details about specific analytical methods are described individually.

## 4. Definition of Analysis Sets and Criteria for Handling in Analysis

## **4.1** Definition of Analysis Sets

The analysis sets in this study are defined as below.

Analysis set	Definition
All enrolled patients	All subjects enrolled in this study
Treated patients	All enrolled patients who received at least 1 dose of the investigational
	product
Full Analysis Set	All treated patients who were evaluated for at least 1 efficacy endpoint
(FAS)	(regardless of whether primary or secondary endpoint) after initiation of
	investigational product administration
Per Protocol Set	All subjects in the FAS, excluding those who met any of the following
(PPS)	conditions:
	• Subjects who were found to fail to meet any of the inclusion criteria after enrollment
	• Subjects who were found to meet any of the exclusion criteria after enrollment
	• Subjects who did not receive sufficient doses of the investigational product (dosing rate at Week 24 < 70%)
	Subjects who used prohibited concomitant medications/therapies
	• Subjects who failed to comply with the dosage regimen of restricted concomitant medications
	• Subjects who were not evaluated for the primary endpoint

Table 4.1Definition of Analysis Sets

If there is any subject for whom there are problems in determination of attribution in the analysis sets, the handling of such subject will be determined through discussion between the sponsor and the medical expert before database lock.

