### 3.2 Subject Randomization and Blinding

### 3.2.1 Randomization Method

This study is a randomized study.

After providing due explanation to each prospective patient and his legal representative, the investigator or subinvestigator will obtain written informed consent/assent, and then prepare a screening log of patients whose legal representative consented to participate in the study in order to check the patient enrollment in the study. After confirming that the prospective patient is deemed eligible by meeting all of the inclusion criteria and none of the exclusion criteria, all necessary information will be entered the Interactive Web Response System (IWRS) and submitted to the Enrollment Center.

Upon completion of enrollment after confirmation of subject eligibility, the subjects will be randomly assigned to the low-dose group, high-dose group, or placebo group in a ratio of 1:1:1 via IWRS based on a dynamic randomization method (minimization method).

Data will be entered in accordance with the description in the IWRS procedure.

The subjects will be stratified by the following randomization adjustment factors:

- Age (between 5 and 6 years, 7 years or older)
- Presence or absence of concomitant steroid use

The above-mentioned enrollment and randomization will be centrally managed; after completion of the enrollment procedure, each subject will be assigned to a treatment group and given an investigational product number to be initially prescribed (for 6-week administration) by the enrollment system.

The investigational product numbers corresponding to subject randomization will be given and reported to the study site with instructions on the investigational product prescription via IWRS. For more detailed information, refer to the IWRS procedure.

If an investigational product not corresponding to the number given via IWRS is prescribed to a subject in error, the IWRS help desk must be notified immediately. In addition, the cause of the erroneous prescription of the investigational product must be recorded at the study site. If a subject receives the investigational product for a different treatment group due to an error in the investigational product number allocation or prescription, the subject will continue to receive the investigational product for the rest of the study period.

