## 2. Target Sample Size and Rationale for the Sample Size

Target sample size: a total of 33 subjects (11 subjects for each group)

Given that DMD is a rare disease that allows only limited recruitment of subjects and that this study is primarily intended to evaluate the efficacy of TAS-205 in an exploratory manner, the sample size was determined not statistically, but based on feasibility.

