## **3.4.2** HANDLING OF MISSING VALUES AND ABNORMAL VALUES

For missing values, no imputation will be applied. Data employed at each time point will be used in analysis. For primary and secondary efficacy endpoints, LOCF or MMRM imputation will be applied as needed. The incidence of adverse events, etc. will be analyzed using the analysis set as the denominator.

All measurement data will be used in analysis, except for abnormal values that can be clearly explained, including laboratory values affected by hemolysis at blood collection. Any abnormal value excluded from analysis will be identified, and the rationale for exclusion will be provided.

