#### **6.1** Analysis of the Primary Endpoint

The following analyses will be performed in the PPS and FAS:

The following analyses will be performed for the primary endpoint, defined as the change from baseline in 6MWD at Week 24: Analysis will also be conducted in the group combining the low-dose group and the high-dose group excluding the analysis of MMRM.

- A 2-sample t-test will be performed between each treatment group and placebo group. This analysis will be performed with and without the LOCF imputation. Analyses will also be conducted with the following baseline definitions.
  - (1) Analysis excluding the subjects for whom the value of (6MWD on Day 1 6MWD at screening)/6MWD at screening is 0.2 or higher or -0.2 or lower
  - (2) Analysis using the mean value of 6MWD on Day 1 and 6MWD at screening as the baseline value
- With respect to the above analysis, subgroup analysis will be conducted for the following items.

Subgroup analysis: Presence or absence of the history of steroid use, age category ( $\geq$ 5 years and <7 years, and  $\geq$ 7 years), and baseline 6MWD (<350 m, and  $\geq$ 350 m)

- The treatment effect will be estimated using the MMRM. The changes from baseline in 6MWD measured at other time points will also be included in this analysis. Covariates will be the assigned group, baseline value, time point, and the interaction term of the assigned group and time point.
- Using the MMRM, the dose relationship will be analyzed with treatment contrasts of (placebo group, low-dose group, high-dose group) = (-2 1 1), (-1 0 1), and (-1 -1 2). The changes from baseline in 6MWD measured at other time points will also be included in this analysis. Covariates will be the assigned group, baseline value, time point, and the interaction term of the assigned group and time point.
- For the above 2 analyses, analyses will be conducted in the PPS by adding age and the presence or absence of the history of steroid use to explanatory variables. In addition, subgroup analysis will be conducted for the following items.

Subgroup analysis: Baseline 6MWD ( $\leq$ 350 m, and  $\geq$ 350 m)

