#### O MMRM

The confidence coefficient for estimation of confidence interval will be 2-sided 95%. In the analysis of MMRM, SAS MIXED procedure will be used as shown in the following SAS code.

proc mixed data = INDATA;

class	ATRTN † (ref='1'[Placebo]) AVISITN † SUBJID † ;
model	$AVAL^{\dagger} = BASE^{\dagger} ATRTN AVISITN ATRTN*AVISITN / ddfm = KR ;$
lsmeans	ATRTN*AVISITN / diff cl alpha = 0.05 ;
repeated	AVISITN / subject = SUBJID type = $UN^{\#}$ ;
estimate	"Low Dose TAS-205 Saturation - Week 12" ATRTN -2 1 1 ‡
	ATRTN*AVISITN $-2\ 0\ 1\ 0\ 1\ 0$ / cl alpha = 0.05;
estimate	"Low Dose TAS-205 Saturation - Week 24" ATRTN -2 1 1 ‡
	ATRTN*AVISITN $0 - 2 0 1 0 1 / cl alpha = 0.05$ ;
estimate	"Placebo vs High Dose TAS-205 - Week 12" ATRTN -1 0 1 ‡
	ATRTN*AVISITN $-100010$ / cl alpha = 0.05;
estimate	"Placebo vs High Dose TAS-205 - Week 24" ATRTN -1 0 1 ‡
	ATRTN*AVISITN $0 - 1 0 0 0 1 / cl alpha = 0.05$ ;
estimate	"High Dose TAS-205 Saturation - Week 12 " ATRTN -1 -1 2 ‡
	ATRTN*AVISITN $-1 \ 0 \ -1 \ 0 \ 2 \ 0 \ / \ cl \ alpha = 0.05$ ;
estimate	"High Dose TAS-205 Saturation - Week 24 " ATRTN -1 -1 2 ‡
	ATRTN*AVISITN $0 - 1 0 - 1 0 2 / cl alpha = 0.05$ ;

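### In the PPS the LOCF t-test of Week 24 6MWD change repeats the observed-case t-test, and the MMRM adjusted for age and steroid history is planned only there, so no such model uses a boy with Week 12 but no Week 24 data

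*SAP*

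**What the plan says.** The primary endpoint is the change from baseline in 6MWD at Week 24 (SAP 5). The PPS is the main efficacy set and the FAS is supplementary (SAP 3.4.6).

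- **Who is in the PPS.** Among the exclusions in SAP 4.1, repeated in Protocol 13.1.2.1, are "Subjects who were not evaluated for the primary endpoint".
- **Missing values.** SAP 3.4.2: "For primary and secondary efficacy endpoints, LOCF or MMRM imputation will be applied as needed". SAP 8.3 defines LOCF as filling a missing last time point from the value before it.
- **T-test.** SAP 6.1 compares each dose with placebo on the Week 24 change, in both PPS and FAS: "This analysis will be performed with and without the LOCF imputation". Protocol 13.1.3.2 says the same.
- **MMRM.** SAP 6.1 plans a model with group, baseline value, time point and their group-by-time interaction, using Weeks 12 and 24, in both PPS and FAS.
- **Adjusted MMRM.** For this model and its dose contrasts, "analyses will be conducted in the PPS by adding age and the presence or absence of the history of steroid use to explanatory variables". A version by baseline 6MWD, split at 350 m, follows under the same instruction. No FAS run is given for either.
- **Sample size.** 33 boys, 11 per group; "the sample size was determined not statistically, but based on feasibility". No SD, effect size or dropout rate is stated.

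**The concern.** LOCF and MMRM are named as the ways of dealing with a missing 6MWD. In the set that carries the main efficacy results, a boy with no Week 24 6MWD has already been taken out, so neither method has him to work on.

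Two things follow. First, the report will show two PPS t-tests that agree because they contain the same boys and values, and a reader may take this for a passed sensitivity check. Second, a boy who walked at Week 12 and then left contributes nothing to any model adjusted for age and steroid history. Those covariates correspond closely to the randomization factors (age group and concomitant steroid use, Protocol 3.2.1), so this is the model nearest to the design.

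Such boys are foreseeable. Assessments at discontinuation cover the safety endpoints (Protocol 10.3 and Table 1, note 16), so an early leaver normally has no Week 24 6MWD. Leaving can also be tied to the outcome, because needing walking aids in the efficacy tests is a discontinuation criterion (Protocol 4.3).

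**Working it through.** **1. Logic of the sets.** A boy in the PPS has been evaluated for the Week 24 change. LOCF changes a value only if the last time point is missing. The LOCF and observed-case data for this endpoint are therefore identical in the PPS.

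**2. The one exception.** SAP 4.2 allows Day 169 ± 7, that is Days 162 to 176, and excludes other values as a rule. Protocol 3.2.2.2 allows the Week 24 evaluation up to 174 + 2 + 2 = Day 178. A boy tested on Day 177 or 178 was arguably evaluated and stays in the PPS, yet his value is excluded as a rule, so LOCF could act. The documents do not settle this case.

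**3. Illustration.** Simulated trials of 3 × 11 boys (invented data), high dose minus placebo, Week 24 change in metres, Week 12 complete:

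| Boys missing Week 24 | PPS t-test, no LOCF | PPS t-test, LOCF | FAS t-test, LOCF | PPS MMRM | FAS MMRM |
|---|---|---|---|---|---|
| 1 | 50.39 | 50.39 | 54.97 | 50.09 | 54.61 |
| 3 | -20.20 | -20.20 | -20.76 | -20.06 | -23.24 |
| 5 | 43.10 | 43.10 | 36.63 | 40.72 | 38.50 |

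The two PPS t-test columns agree in every row. The FAS results move because only there do the leavers' Week 12 values enter.

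**4. How often the rule bites.** If a proportion d of boys lack a Week 24 6MWD, the expected number removed by this condition alone is 33d, and the chance of at least one is 1 − (1 − d)^33. For d = 5%, 10%, 15% and 20% (assumed) this gives 1.7, 3.3, 5.0 and 6.6 boys, and 82%, 97%, 99.5% and 99.9%.

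**5. Possible size of the error.** Assumptions: SD of change 40 m at Week 12 and 60 m at Week 24; correlation 0.7; true Week 24 difference 20 m; boys in the worst third of their arm at Week 12 miss Week 24 with probability p, and nobody else does. For a normal variable the worst third averages 1.091 SD below the mean, so the Week 24 mean of an arm's completers is too high by

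shift = 0.7 × 60 × 1.091 × (p/3) / (1 − p/3).

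- p = 0.25 (8% of the arm missing): 42 × 1.091 × 0.0833/0.9167 = 4.2 m
- p = 0.30 (10%): 42 × 1.091 × 0.10/0.90 = 5.1 m
- p = 0.50 (17%): 42 × 1.091 × 0.1667/0.8333 = 9.2 m

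The completers' difference is 20 − (placebo shift) + (active shift):

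| Missing on placebo | Missing on active | Completers' estimate |
|---|---|---|
| 10% | 0% | 14.9 m |
| 17% | 0% | 10.8 m |
| 17% | 8% | 15.0 m |
| 8% | 17% | 25.0 m |
| equal | equal | 20.0 m |

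Simulation with 11 per arm gives essentially the same figures. A likelihood estimate that keeps the Week 12 values averages about 20 m in the unequal scenarios. Its sampling SD is about 26 m, the same as for completers only (60 × √(2/11) = 25.6 m with nobody missing).

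**The case against.** Much of the case on the other side stands.

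- **The two rules do not contradict each other.** SAP 6.1 applies one list of analyses to two sets, and SAP 3.4.2 says LOCF or MMRM is used as needed. Where nothing is missing, LOCF does nothing. That is a redundant table, not an impossible instruction.
- **The FAS already covers most of it.** It keeps any treated boy with a post-dose efficacy evaluation, and the LOCF t-test, unadjusted MMRM and dose contrasts all run there. The gap left is the adjusted model.
- **The primary analysis would not move.** It is summary statistics of the Week 24 change by group. A boy with no Week 24 value adds nothing to it, whether or not he is formally in the PPS.
- **Other conditions may remove the same boys.** Walking aids in motor tests and persistent ventilation are prohibited therapies (Protocol 7.4.1), and their use is a separate PPS exclusion.
- **The bias figures are assumed.** In a further simulation with equal missingness in both arms, the completers' estimate was 18.3 to 20.2 m against 20 m. If missingness depends on the unseen Week 24 value, the likelihood estimate is itself short, at 13.5 to 16.4 m. A 5 to 9 m error is also small beside a sampling SD of 26 m in a study to be judged on numerical trends (Protocol 14.1).

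A reader might infer that every PPS result is complete-case. The documents do not support that. The PPS does not require CT, timed tests, strength, pulmonary or urine data to be complete, so LOCF and MMRM still act on those endpoints, and the PPS MMRM of 6MWD keeps a boy who lacks only Week 12.

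**Conclusion.** The point holds in a limited form. For Week 24 6MWD, the PPS t-test with LOCF repeats the one without it, apart from a possible out-of-window test, and their agreement is not evidence of robustness. The PPS MMRM cannot use the Week 12 value of a boy with no Week 24 test. Because the version adjusted for age and steroid history is confined to the PPS, no such model of 6MWD uses partial data.

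A reader might go on to conclude that the PPS estimate is biased towards no effect. The documents give no basis for a direction. Under the assumptions in step 5, the error is about 5 to 9 m of a 20 m effect: towards no effect if outcome-related missingness is heavier on placebo, away from it if heavier on active, and near zero if equal. With no missing Week 24 test there is no error. The size also depends on how many of the boys concerned meet the other PPS conditions.

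Nor do the documents show that the condition has to go. Requiring the primary measurement is a common per-protocol rule and is openly stated here. Since the primary analysis is descriptive and the FAS runs exist, this is worth correcting but does not threaten the study's main result.

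**What to change.** In SAP 6.1:

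1. Plan the MMRM adjusted for age and steroid history, with its dose contrasts, in the FAS as well as the PPS. Extending the 350 m subgroup version is optional at this sample size.
2. Drop the PPS t-test of Week 24 6MWD change with LOCF, or keep it with a note that it carries no information about missing data. Point the reader to the FAS LOCF and MMRM results.
3. Report n per arm for each of these analyses.

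The PPS definition can stay as it is.

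The cost is one additional set of model outputs and no new data. Labelling the t-test needs only SAP wording. Dropping it would also mean aligning Protocol 13.1.3.2, which orders it in the PPS.

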## **4.2** Criteria for Handling in Analysis

- If it is questionable as to how some subject data are to be handled, the sponsor will discuss the case(s) with the medical expert to make a decision before key code breaking.
- Data from subjects who have been administered the investigational product different from their randomized investigational product will be handled as data for the actually administered investigational product in the analysis of treated patients or PPS.
- In the analysis of FAS, the data will be handled as data for the randomized investigational product.
- Evaluation made in the period other than the period of clinical assessments stipulated in the protocol will be excluded as a rule (Table 4.2). If the evaluation is included in the analysis, the fact should be stated clearly. If examination is conducted twice or more during the period, the examination closest to the stipulated date will be adopted.

Table 4.2 Termissible Range for Chinear Assessments		
Stipulated days	Permissible range	
Baseline period	Within 2 weeks after enrollment	
Day4	±1 day	
Day6	Day 6 only	
Day15	+5 days*	
Day29	$\pm 5$ days	
Day57, Day127	±7 days	
Day85, Day169	±7 days	
Follow-up period (21 days after the end of investigational product administration)	±7 days	

Table 4.2 Permissible Range for Clinical Assessments

\* If all the days in the permissible range are holidays/national holidays and clinical assessments cannot be performed, the first working day after the holidays/national holidays is permitted.

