# Table 1 Clinical Assessment Schedule

- 1. Permissible range for clinical assessments: After Day 1 (except for the follow-up and discontinuation tests), clinical assessments will be performed as specified in Section 5.1.10. The permissible range for the 2nd (Week 12) and 3rd hospitalization (Week 24) will be the standard hospitalization day ± 7 days. For hospitalization on any day other than the standard hospitalization day, pooled urine will also be started on the day after hospitalization, and the efficacy evaluation including that of motor function (hereinafter referred to as the efficacy evaluation), will be performed on the end day of pooled urine. However, if the efficacy evaluation cannot be performed on the end day of pooled urine to an adverse event or any other reason, the efficacy evaluation may be performed within the end day of pooled urine + 2 days (this permissible range for the efficacy evaluation will also apply to the baseline evaluation). The increase in the number of hospitalization day at ue to the delay of the efficacy evaluation (excluding prolonged hospitalization due to inpatient treatment) will not be assessed as a serious adverse event. For hospitalization within the permissible range of standard hospitalization day at Week 24 (Day 167) ± 7 days (Day 160 to Day 174), the investigational product will not be administered after the efficacy evaluation.
- 2. Subject ID code entry: A unique subject ID code will be provided to each patient whose legal representative has received an explanation of informed consent (the patient should also receive an explanation of informed consent/assent whenever possible).
- 3. Body weight: No dose increase/decrease will be considered according to body weight increase/decrease during the study.
- 4. Hospitalization: In principle, the duration of the initial hospitalization (Day -2 to Day 6) will be 8 days and 7 nights. In principle, the discharge day for the 2nd hospitalization (hospitalized on Day 83 and discharged on Day 85) and the 3rd hospitalization (hospitalized on Day 167 and discharged on Day 169) will be the day of the efficacy evaluation; however, subjects who visit the site from afar may be discharged on the day after the efficacy evaluation. Subjects will be appropriately instructed before hospitalization to bring all the prescribed investigational products (managed by their legal representatives) and subject medication diary at each hospitalization.

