## 5.1.10 Timing for Individual Evaluations/Tests

- · Screening period (for eligibility confirmation): Performed within 14 days before enrollment
- · Baseline period (for baseline evaluation): Performed within 14 days after enrollment
- · Administration period:
- Day 4: Performed within  $\pm 1$  day (pooled urine may also be started on Day  $4 \pm 1$  day)
- Day 6: Performed on the day
- Day 15: Performed within  $+ 5 \text{ days}^{*1}$ 
  - \*1 If all the days in the permissible range are holidays/national holidays and clinical assessments cannot be performed, the first working day after the holidays/national holidays is permitted.
- Day 29: Performed within  $\pm$  5 days
- Day 57, 127: Performed within  $\pm$  7 days
- Day 85, 169: Performed within  $\pm$  7 days (if hospitalization is within the permissible range of  $\pm$  7 days)
- Follow-up period: Follow-up test (21 days after the end of investigational product administration): Performed within  $\pm 7$  days

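### SAP Table 4.2 leaves out the protocol's two-day efficacy allowance, so its exclusion rule, applied literally, would drop some protocol-permitted 6MWD tests

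*SAP*

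**What the plan says.** SAP Section 4.2 sets a default exclusion: "Evaluation made in the period other than the period of clinical assessments stipulated in the protocol will be excluded as a rule". It refers to Table 4.2, which gives baseline as "Within 2 weeks after enrollment" and Days 85 and 169 as ±7 days. It leaves room for exceptions: "If the evaluation is included in the analysis, the fact should be stated clearly". Doubtful data go to the sponsor and the medical expert before key code breaking. SAP Section 4.1 has a similar route for analysis sets: "the handling of such subject will be determined through discussion between the sponsor and the medical expert before database lock". The PPS leaves out "Subjects who were not evaluated for the primary endpoint".

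The protocol gives the timing in several places:

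- Section 5.1.10 reads "Baseline period (for baseline evaluation): Performed within 14 days after enrollment". For Days 85 and 169 it gives ±7 days with the condition "if hospitalization is within the permissible range of" ±7 days. It does not mention an extra two days.
- Table 1 note 1 says that, if the evaluation cannot be done on the planned day, "the efficacy evaluation may be performed within the end day of pooled urine + 2 days". It extends this to baseline. The footnote to the period definitions in Section 3.1.1 repeats the allowance.
- Table 1 note 14 lets Day 1 fall as late as 16 days after enrollment.
- Section 3.2.2.2 names Day 178 as the last allowed day for the Week 24 efficacy evaluations, and the fourth drug allocation is sized to cover it.

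**The concern.** Table 4.2 follows protocol Section 5.1.10, drops its hospitalization condition for Days 85 and 169, and does not carry over the two-day allowance. The table does reproduce the Day 15 holiday exception, so a programmer could reasonably take it as complete. Tests that the protocol permits, and for which drug was supplied, would then be out of window.

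The primary analysis is a set of summary statistics on the Week 24 change in 6MWD in the PPS, repeated in the FAS. A boy whose baseline or Week 24 test is excluded has no such change without LOCF. The SAP does not say whether a window-excluded test counts as not evaluated for PPS membership, or what replaces an excluded baseline. A lost Week 12 test touches the Week 12 secondary analysis, the MMRM and any value carried forward. Protocol Section 11.2 puts the other motor tests, muscle strength and BIA on the same day, so those results could be excluded with the 6MWD. Protocol Section 14.1 expects efficacy to be judged on numerical trends, so the arm means carry the weight.

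**Working it through.** **Inputs.** Permitted admission: Days 76–90 and Days 160–174 (protocol Section 3.1.1), and within 12 days after enrollment for baseline (Table 1 note 13). Urine pooling starts the day after admission and ends the next morning, so the planned test day is admission + 2. Permitted delay: 0, 1 or 2 days (Table 1 note 1). Table 4.2 limits: day 14 after enrollment, 85 + 7 = Day 92, and 169 + 7 = Day 176.

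**Formula.** Test day = admission day + 2 + delay.

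**The protocol's own figure.** 167 + 7 + 2 + 2 = Day 178, which agrees with Section 3.2.2.2.

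| Visit | Latest test, no delay | Latest test, full delay | Table 4.2 limit | Permitted days outside |
|---|---|---|---|---|
| Baseline (days after enrollment) | 12 + 2 = 14 | 12 + 2 + 2 = 16 | 14 | 15, 16 |
| Week 12 | 90 + 2 = Day 92 | 90 + 2 + 2 = Day 94 | Day 92 | 93, 94 |
| Week 24 | 174 + 2 = Day 176 | 174 + 2 + 2 = Day 178 | Day 176 | 177, 178 |

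The baseline limit of 16 agrees with note 14. Undelayed tests, and the end of urine pooling, are always inside Table 4.2. So is an admission on the standard day with the full delay: 167 + 2 + 2 = Day 171.

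**How narrow the trigger is.** List every permitted pair of admission day and delay.

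- Week 24: 15 × 3 = 45 pairs, 30 of them with a delay. Outside: 173 + 2 + 2 = 177, 174 + 2 + 1 = 177 and 174 + 2 + 2 = 178. That is 3/45 = 6.7%, or 3/30 = 10% of delayed pairs.
- Week 12: 89 + 2 + 2 = 93, 90 + 2 + 1 = 93 and 90 + 2 + 2 = 94. The fractions are the same.
- Baseline, admission on days 1–12: 36 pairs, 24 with a delay. Outside: 11 + 2 + 2 = 15, 12 + 2 + 1 = 15 and 12 + 2 + 2 = 16. That is 3/36 = 8.3%, or 3/24 = 12.5%. If the enrollment day counts as an admission day, 3/39 = 7.7% and 3/26 = 11.5%.

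These are counts of permitted days, not probabilities.

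**Scale of losing one boy, for any reason.** With 11 per arm (SAP Section 2), one boy is 1/11 = 9.1% of his arm. If his change differs from the mean of the other 10 by k SD, the arm mean moves by k/11 SD. For an assumed k of 1 to 2 that is 0.09 to 0.18 SD. Divided by the standard error of 1/√11 = 0.302 SD, it is 0.30 to 0.60 standard errors. This is a generic yardstick and says nothing about how often the rule would apply.

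**The case against.** The strongest reply is that the SAP sentence points to the protocol, and the protocol includes note 1. The title of Table 4.2 nearly matches the heading of that note. On this reading a delayed test within note 1 is in window, and the table is only an incomplete summary. The baseline part is weaker still: protocol Section 3.1.1 gives the 14 days only in principle, the actual start day is designated Day 1, and SAP Section 6.1 calls the baseline measurement the Day 1 value. Any remaining doubt can be settled before unblinding.

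Much of this stands. A reader might infer that permitted tests will certainly be discarded. The documents do not support that, because exclusion is a default with stated exceptions. A reader might also infer that an excluded baseline necessarily removes the boy from the LOCF analyses and the MMRM. Both use a baseline value, but a screening 6MWD exists for every boy, SAP Section 6.1 already uses it in one alternative baseline, and no fallback rule is given either way. Removal is possible but not stated.

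What the reply does not remove is the mismatch. The rule names a table whose limits are shorter than the protocol's, and protocol Section 5.1.10 is itself silent on the allowance. Leaving this to case discussion makes inclusion in the primary analysis a matter of judgment on something the protocol already decides.

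**Conclusion.** The inconsistency is real and should be corrected, but its likely effect is small. Applied literally, Table 4.2 would exclude permitted efficacy tests on days 15–16 after enrollment, Days 93–94 and Days 177–178. This happens only with admission in the last two permitted days and a delayed test, and the number of boys affected cannot be known from the documents. The loss of the Week 24 change score rests on three assumptions: the table is read literally, an excluded test is treated as absent, and no one overrides the rule.

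A reader might infer a bias between arms, because delays may follow adverse events. The documents give no basis for a direction, and none is claimed. Nor is an error rate at stake, because the primary analysis is descriptive. The 0.30 to 0.60 standard errors describe losing any one of 11 boys under an assumed deviation, not the expected effect of this rule.

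**What to change.** Before key code breaking:

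1. Reconcile protocol Section 5.1.10 with Table 1 notes 1 and 14 and with Section 3.2.2.2.
2. In SAP Table 4.2, for efficacy evaluations only, define the window by the protocol's existing conditions: admission within the permitted range (Days 76–90, Days 160–174, or within 12 days after enrollment for baseline), the test no later than two days after urine pooling ends, and the baseline test before the first dose. The latest days are then Day 94, Day 178 and day 16 after enrollment.
3. State that a test meeting these conditions counts as evaluated for the primary endpoint when PPS membership is decided.

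Simply widening the table to Days 78–94 and 162–178 would go too far. It would accept a boy admitted on Day 91, outside the permitted range, with an undelayed test on 91 + 2 = Day 93. The laboratory, ECG and pooled-urine windows should stay as they are unless the protocol is clarified for them: Table 1 notes 6 and 7 set only the order of the laboratory and ECG assessments on the efficacy day, and urine pooling already ends inside the table's limits.

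The cost is one protocol clarification, two revised table rows and one sentence. No new data are needed. The only downside is that tests up to two days later are accepted, which the protocol already permits.
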